1.1.2 Autosomal Dominant CNM

The clinical phenotypes of ADCNM range from mild and moderate forms in adult patients to severe forms in infants. In general, adolescent and young adult patients with moderate phenotype have moderate skeletal muscle weakness associated with ptosis and ophthalmoplegia and had delayed motor milestones as children. Pediatric patients usually have generalized weakness, hypotonia, moderate degree of facial weakness with open mouth, ptosis, and ophthalmoplegia (Romero and Bitoun, 2011). Many children with the disease also have stiff joints and sideways curvature of the spine (scoliosis). In childhood, as in the neonatal period, there is a risk of respiratory failure which can become life-threatening in serious situations (e.g. if the patient develops pneumonia). Adults may experience respiratory failure, which in turn may cause cardiac insufficiency. A significant portion of patients become wheelchair-dependent in their fifties (Bitoun et al., 2005; Verhaart et al., 2017a; Verhaart et al., 2017b; [name], 2017).

ADCNM is caused by mutations in the *DNM2* gene on chromosome 19p13.2 (Bitoun et al., 2005). Dynamins are structurally complex proteins composed of 5 different domains. CNM-causing mutations identified to date mainly localize to the middle domain involved in protein self-assembly and centrosome localization.

The incidence of ADCNM is currently unknown, although it has been reported to account for approximately 50% of CNM cases (Romero, 2010). The patient pool is estimated to have 553 prevalent cases worldwide (Vandersmissen et al., 2018). No NHS data of ADCNM have been published to date.

The prognosis of ADCNM is currently unknown. However, it appears to be quite heterogeneous, with some patients exhibiting a rapid deterioration and others a slow progressive loss of muscle function.

1.2 RNA-targeted Therapeutic Concept

Antisense oligonucleotide (ASO) technology represents a promising therapeutic approach for diseases caused by gain-of-function mutations. It either reduces expression of the mutant gene or induces the production of a functional or partially functional protein through a number of mechanisms including splicing modulation for loss-of-function genetic diseases. In neuromuscular diseases, this approach has been mainly applied to dystrophic muscle diseases where uptake may be facilitated by disruption of membrane integrity, or to diseases with nuclear accumulation of pathogenic RNA that favors RNase H1-dependent degradation of the targeted transcript (Wheeler et al., 2012).

As *MTM1* and *DNM2* are involved in membrane remodeling and membrane trafficking, impairment of these processes could be a common CNM pathomechanism. The physiological interplay is complex and not completely understood. *MTM1* and *DNM2* function in a common pathway, where either loss-of-function mutations in *MTM1* or gain-of-function mutations in *DNM2* lead to the CNM phenotype. *MTM1* is a regulator of *DNM2* in skeletal muscle in vivo (Cowling et al., 2014).

Nonclinical data in mouse models of XLCNM and ADCNM have demonstrated a rescue of the CNM phenotype by reducing *Dnm2* mRNA (Cowling et al., 2014; Tasfaout et al., 2017; Buono et al., 2018).

Based on these nonclinical results, the sponsor has decided to develop DYN101, an ASO targeting reduction of human *DNM2* mRNA, for subjects with mutations in *MTM1* (XLCNM) and mutations in *DNM2* (ADCNM).

1.3 Investigational Medicinal Product Background

Mutations in the *DNM2* gene or genes upstream of *DNM2* in the molecular pathway result in higher activity of DN2 protein (either by activation or higher accumulation of the protein), which in turn plays a critical role in manifestation of CNM of different types in pediatric and adult patients (Cowling et al., 2014; Cowling et al., 2017; Buono et al., 2018).

A summary of the experiments with DYN101 is provided below. For detailed information on DYN101, refer to the latest version of the Investigator's Brochure (IB) (Dynacure).

Compatibility of DYN101 200 mg/mL eq. sterile solution with the selected infusion solution and the selected infusion tubing for clinical study DYN101-C101, was evaluated in a compatibility study. The compatibility study mimicked the worst-case interaction of DYN101 200 mg/mL eq. sterile solution with tubing, infusion solution and infusion bag.

The compatibility study evaluated both the physico-chemical and chemical stability of DYN101 in the infusion solution after adding, after 6 hours and after 24 hours. Two infusion bags were prepared (3.5 mL DYN101 added to 250 mL sodium chloride 0,9%) and 20 mL samples were taken through the tubing at T0. The prepared infusion bags were stored at room temperature and at T6h (bag 1) and T24h (bag 2), a second 20 mL sample per bag is taken through the tubing. Test parameters were appearance, pH, viscosity, assay DYN101, chromatographic purity and osmolality, determined at time points 0, 6, and 24 hours.

No physico-chemical or chemical degradation was observed in any of the samples tested in the compatibility/stability study. Based on the test results obtained in the study, it can be concluded that the proposed study set-up, using 1-mL or 3-mL syringes with luer lock, together with 0.9% sodium chloride infusion bags and the proposed infusion tubing is compatible with the DYN101 solution.

1.3.1 Nonclinical Information

Potency and efficacy of DYN101 were tested in vitro in human cell lines and in vivo in transgenic mice expressing human *DNM2*. Tolerability and safety were assessed in rodents (mice, rats) and in non-human primates (NHP). Single nucleotide polymorphism and off-target analysis was done in silico and in vitro.

Proof-of-concept studies in mouse CNM disease models have demonstrated the efficacy of *DNM2* mRNA targeting, *DNM2* protein level reduction and disease improvement/stabilization. Reduction of *DNM2* mRNA was already seen 1 week after dosing. In addition, pharmacology/tolerability and toxicity studies in mice, rats, and Cynomolgus monkeys have demonstrated the safe dosing of DYN101 up to/higher than the targeted human dose levels.

In general, ASOs show a fast distribution (minutes to hours) into tissue, a rapid transmission into cells and long half-lives (2-4 weeks). In addition, pharmacokinetic (PK) properties of ASOs are similar across species (Yu et al., 2013) especially NHP PK data can be used to predict human PK behavior, including steady state in humans. Based on toxicokinetic results of a 13-week NHP study, DYN101 exposures increased in a dose-dependent manner with only moderate accumulation. As typical for ASOs, the subcutaneous (SC) administration of DYN101 exhibited a fast absorption ($t_{max}=2$ hours) with lower C_{max} in comparison to the intravenous (IV) group and 100% bioavailability based on AUC. After reaching C_{max} , DYN101 concentration decreased in a biphasic manner with a fast-distributional half-life ($t_{1/2}$) and a slower terminal elimination $t_{1/2}$ of 21 days (see Section 3.2.1 of the IB). A population PK modeling and simulation approach showed 90% of steady state concentration will be reached with the planned dosing regimen (weekly administrations in MAD part), after 6 weeks, justifying a biopsy sample taken for early drop outs (see Section 3.1.2).

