- Where possible, the visits in the MAD part will take place on the same day of the week as Day 1 (and of the SAD part, if applicable). A window of ±3 days is allowed for visits as of Week 3, with a minimum of 4 days between 2 subsequent infusions. Assessments of a single visit can be split over 2 consecutive days, if required.
- Replacement subjects starting in the MAD part should sign an ICF for participation in the MAD part, and their eligibility will be assessed (see Trial Schedule for the Screening Period) before the first IMP administration in the MAD part (MAD Week 1 Day 1). If needed (to be discussed with the sponsor), these subjects will have a run-in period before they can start in the MAD part (see Trial Schedule for Run-in Period). A DNA sample (optional) and a muscle biopsy should be taken before the first IMP administration. If needed, replacement subjects in MAD1 and MAD2 may have the second muscle biopsy taken after 6 to 12 weeks of MAD treatment, after discussion with the sponsor.
- All assessments need to be done pre-dose.
- Slow infusion over 1 hour; subjects will be monitored on site by qualified site personnel for a minimum of 1 hour after the infusion for safety. Platelet counts as determined by the local laboratory need to be within normal ranges before IMP administration.

- e) A symptom-directed physical examination (and measurement of body weight at MAD Week 1 Day 1) will be performed.
- f) During an unscheduled visit which will occur between 6 weeks and 7 days prior to the baseline visit for subjects for whom the last visit in the SAD part will be more than 3 months before the baseline visit in the MAD part.
- g) To be performed pre-dose.
- h) Only applicable if a liver ultrasound and/or hepatic elastography was not performed during the screening period.

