3.1.2 Replacement of Subjects

Enrolled subjects who are withdrawn (see Section 4.5) can be replaced after discussion with the sponsor, the medical monitor and the investigator in the following circumstances:

- Enrolled subjects who participated in the SAD part and drop out before the start of the MAD part can be replaced (for the MAD part).
- Enrolled subjects who drop out and received less than 6 weeks of MAD treatment can be replaced.
- Enrolled subjects who drop out but received between 6 and 12 weeks of MAD treatment and do not consent to a second muscle biopsy can be replaced. However, subjects will not be replaced if they received between 6 and 12 weeks of MAD treatment and consent to a second muscle biopsy, or if they received more than 12 weeks of MAD treatment.

There will be stand-by subjects for replacement of subjects who discontinue the trial early, if needed. Stand-by subjects will perform run-in visits until the last MAD subject has completed Week 13, unless needed for replacement.

Replacement subjects starting in the MAD part should sign an ICF for participation in the MAD part, and their eligibility will be assessed before the first IMP administration in the MAD part (MAD Week 1 Day 1). Replacement subjects may or may not need a run-in period, in consultation with the sponsor. A muscle biopsy and a DNA sample should be taken before the first IMP administration. If needed, replacement subjects in MAD1 and MAD2 may have the second muscle biopsy taken after 6 to 12 weeks of MAD treatment, after discussion with the sponsor.

Further details will be described in the site manuals (e.g. Laboratory Manual, Site Operations Manual, Pharmacy Manual).

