### **6.13.8 Muscle Biopsy**

Descriptive statistics (n, mean, SD, median, min, max) of the observed values and change from baseline will be presented by treatment group (cohort, subcohort) and visit.

All data will be listed.

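### The 90%-of-steady-state figure that justifies 6-week muscle biopsies names no matrix and is unsupported for muscle; the SAP averages early-withdrawal biopsies with Week 13 biopsies, which would pull means down

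*Protocol*

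**What the plan says.** Protocol 1.3.1 describes monkey data in which "DYN101 concentration decreased in a biphasic manner", with a fast distribution phase and a "slower terminal elimination $t_{1/2}$ of 21 days". It gives 2 to 4 weeks as the usual half-life range for this drug class and reports that "DYN101 exposures increased in a dose-dependent manner with only moderate accumulation". It then credits a population PK simulation with the finding that "90% of steady state concentration will be reached with the planned dosing regimen (weekly administrations in MAD part), after 6 weeks", and offers this as the reason for biopsying early drop-outs. No matrix and no model parameters are given. Protocol 3.2.5 places steady state at 12 weeks, the planned time of the second biopsy.

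Protocol 3.1.2 lets earlier biopsies stand in for the planned one: "subjects will not be replaced if they received between 6 and 12 weeks of MAD treatment and consent to a second muscle biopsy". For replacements, the same section and the footnote to the MAD schedule say that "replacement subjects in MAD1 and MAD2 may have the second muscle biopsy taken after 6 to 12 weeks of MAD treatment", if needed and after discussion with the sponsor.

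SAP 6.2.4 assigns early-withdrawal data to the next scheduled visit for that variable, which for the second biopsy is MAD Week 13. SAP 6.13.8 says that biopsy statistics "will be presented by treatment group (cohort, subcohort) and visit", with no reference to doses received. No visit rule is stated for replacements biopsied at 6 to 12 weeks.

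**The concern.** The 90% figure and the 21-day half-life stand close together in Protocol 1.3.1, and simple accumulation at that half-life does not give 90% at 6 weeks. The figure is used for muscle, yet nothing in the documents shows that it describes muscle.

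The second biopsy is the trial's measure of target engagement (Protocol 6.2.6). It was to feed the fourth IDMC review, which covers the opening of MAD3 and a recommendation on the paediatric study's starting dose (Protocol 3.1.1). If some biopsies come after 6 weekly doses and others after 12, a dose group's mean muscle concentration and knock-down fall for a reason unrelated to dose level. The IDMC may decide by sub-cohort, and an MTM1 sub-cohort has at most 3 subjects, so one early biopsy carries real weight there.

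**Working it through.** **Inputs.** Half-life 21 days, class range 14 to 28 days, 90% at 6 weeks (Protocol 1.3.1); weekly dosing; effective mouse-muscle concentrations of 3.62, 1.55 and 0.7 µg/g for 50%, 30% and 15% knock-down (Protocol 3.2.5, Table 1 footnote); about 6 subjects per cohort and up to 3 MTM1 subjects per sub-cohort.

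**1. Does the half-life alone give 90%?** With one exponential and half-life h in days, the share of steady state after n weekly doses is 1 − 2^(−7n/h).

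| Half-life | 6 weeks | 10 weeks | 12 weeks | Weeks to 90% |
|---|---|---|---|---|
| 14 d | 87.5% | 96.9% | 98.4% | 6.6 |
| 21 d | 75.0% | 90.1% | 93.75% | 9.97 |
| 28 d | 64.6% | 82.3% | 87.5% | 13.3 |

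Reaching 90% takes log2(10) = 3.32 half-lives, so 90% at 42 days needs a half-life of 42/3.32 = 12.6 days, below the class range. The half-life alone does not reproduce the 90%.

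**2. Can a biphasic model give it?** Let f be the terminal phase's share of AUC (not in the documents; assumed), with the fast phase gone within a week. Average plasma concentration at 6 weeks is then 1 − f × 2^(−6/3) of steady state. At f = 0.4 this is 1 − 0.4 × 0.25 = 90%; f from 0.2 to 1.0 gives 95% to 75%. AUC accumulation is 1/(1 − f × 2^(−1/3)): 1.47-fold at f = 0.4 and 4.85-fold at f = 1. So 90% for average plasma can coexist with a 21-day terminal half-life. The pre-dose plasma level, however, is still only 75% to 77% of steady state at f = 0.4 if the distribution half-life is 1 day or less (82% at 2 days).

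**3. A 6-week biopsy relative to a 12-week one.**
- Muscle follows the 21-day phase: 0.75/0.9375 = 80% (89% at 14 days, 74% at 28 days).
- The protocol's 90% is taken as true for muscle, with exponential approach: the 12-week share is 1 − 0.1² = 99%, and 0.90/0.99 = 91%.
- Later biopsies, 21-day phase: 0.8425/0.9375 = 90% at 8 weeks and 0.9008/0.9375 = 96% at 10 weeks.

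**4. Knock-down.** Take C/(C + 3.62). It returns 30.0% at 1.55 µg/g (stated 30%) and 16.2% at 0.7 µg/g (stated 15%), so it is a fair approximation.
- 12-week knock-down 50% (C = 3.62): 0.80/1.80 = 44.4%; 0.909/1.909 = 47.6%.
- 12-week knock-down 30% (C = 1.55): 1.24/4.86 = 25.5%; 1.41/5.03 = 28.0%.

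**5. Group mean concentration, 21-day phase.** Each 6-week biopsy is 20% low.
- One of six: 0.20/6 = 3.3% lower.
- Two of six: 6.7% lower.
- One of three (MTM1): 6.7% lower.

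With the 91% ratio, one of six costs about 1.5% and two about 3%.

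**6. Delay after the last dose.** At 21 days, each extra week multiplies the concentration by 2^(−1/3) = 0.79. Days since last dose therefore matter as well as doses received.

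**The case against.** The strongest reply is that the 75% comes from a one-compartment formula applied to a drug that the protocol calls biphasic, while the 90% is attributed to a simulation. One compartment at 21 days would imply 4.85-fold accumulation, which sits badly with monkey data described as showing only moderate accumulation. This stands. A reader might infer that the protocol has made an arithmetic error, or that target engagement is shown to be understated. Neither follows: step 2 shows that the two figures can coexist for average plasma, no muscle half-life is given, and the modelling report is not among the documents.

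The reply does not settle the use of the figure for muscle. The planned biopsy falls about 7 days after the Week 12 infusion, and Protocol 1.5 puts the distribution phase at roughly 24 to 48 hours, so the fast phase should be over. In a linear two-compartment model the tissue compartment then follows the slow phase. That is a reason to expect slow accumulation in muscle, not evidence of it.

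Other points have weight. Early biopsies are a salvage measure in an ultra-rare disease. The shift is small beside sampling error: if the 9.8 ± 2.9 in Protocol Table 1 is mean and SD (not stated), the CV is about 30% and the standard error with six subjects about 30%/√6 = 12%. Drug and mRNA are both measured in the biopsies, so a concentration–response model is less affected than a dose-group mean. Biopsy and dosing data are planned to be listed, so early cases could be found by hand. These points limit the size of the problem; they do not remove a shift that goes one way in a planned by-dose summary.

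**Conclusion.** The concern holds in limited form. The 90% has no stated matrix or model, and the documents do not support it for a muscle sample taken about a week after a dose. Averaging early-withdrawal biopsies with Week 13 biopsies follows from SAP 6.2.4 and 6.13.8 read together; for replacements the SAP is silent.

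The shift is downward even if the protocol's own 90% is accepted: a 6-week biopsy shows about 91% of the 12-week concentration, against about 80% if muscle follows the 21-day phase. The lower figure assumes slow-phase accumulation in muscle, and both assume a sample at exactly 6 weeks. Biopsies at 7 to 12 weeks have a smaller effect, and a delay after the last dose has a larger one.

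Severity is minor to moderate. The trial ended before the interim analysis (SAP 7), the biopsy listing is struck from the abbreviated report (SAP 12), and biopsy is not among the efficacy parameters selected for it (SAP 10). The use mainly affected is the planned fourth IDMC review.

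**What to change.** 1. In Protocol 1.3.1, state the matrix and the model behind the 90%, limit the claim to that matrix, and reconcile it with the 21-day half-life and with the 12-week statement in Protocol 3.2.5.
2. In SAP 6.13.8 and the output for the fourth IDMC review, exempt biopsies from the visit reassignment in SAP 6.2.4, and state how replacement biopsies are labelled.
3. Report each biopsy with the number of weekly doses received and the days since the last dose. Give the Week 13 mean both with and without biopsies taken before the planned 12 weeks of dosing.

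A fixed cut-off at 10 doses is not recommended: it would rest on the one-exponential formula, whereas the protocol places its own 90% at 6 weeks.

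The cost is a clarification in the protocol text and a tabulation rule in the SAP, with no new biopsies. The mean without early biopsies may rest on one or two fewer subjects, which is why both means should be shown.

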1.3.2 Clinical Information

No clinical studies have been conducted with DYN101 so far.

1.4 Rationale for the Trial

There are no available treatments aside from supportive care for patients with CNM. This first-in-human trial with DYN101 aims to assess the safety, tolerability, PK and pharmacodynamics (PD)/preliminary efficacy of DYN101 in subjects ≥ 16 years of age with CNM caused by mutations in *DNM2* or *MTM1*. Targeted lowering of *DNM2* is a novel therapeutic approach and is expected to benefit these patients. *DNM2* protein is ubiquitously present in human cells and elevations in *DNM2* protein levels or *DNM2* function have been demonstrated in muscle tissue in preclinical models and in human tissue from CNM patients. Preclinical models of these mutations have shown the potential of reducing *DNM2* mRNA to prevent and reverse the clinical status. [REDACTED]

[REDACTED] A translation of similar changes in efficacy parameters in these knock-out mouse models to patients has been demonstrated by *MTM1* gene therapy in an ongoing clinical trial conducted by Audentes Therapeutics in patients with XLCNM up to 4 years of age (ASPIRO trial, ClinicalTrials.Gov Identifier: NCT03199469). Moreover, an increased uptake of ASO was seen in muscle of diseased mice over their wild-type counterparts. This first-in-human trial for DYN101 will therefore be conducted in patients and not in healthy volunteers to assess safety, PK and dose selection based on PD/preliminary efficacy.

1.5 Risk/Benefit Considerations

As this trial is investigational, there is no defined, expected benefit for subjects who participate in this trial except a better knowledge of their pathology, and the knowledge that they contribute to RNA-targeted therapy for CNM patients carrying *MTM1* and *DNM2* mutations. Should a clear benefit be shown, the sponsor will consider prolonging therapy for those who participated in the trial.

Due to the encouraging results in animal models of the disease, the translation of changes in efficacy parameters from animals to humans seen in the ongoing gene therapy trial conducted by Audentes Therapeutics (see Section 1.4), and a minimum treatment duration of 24 weeks in this trial, it is possible that subjects may exhibit some clinical benefits during the multiple ascending dose (MAD) or MAD extension.

The risks as described in the following paragraphs are considered to be potential risks to trial subjects, based on what is known about ASOs and the mechanism of action of DYN101. The choice of the eligibility criteria and assessments for this trial in relation to risk mitigation is explained in Section 3.2.

Although this will be the first trial with an ASO specifically directed at lowering *DNM2* mRNA, it can be expected that similar ASO-platform toxicities could occur (adverse events [AEs] of special interest, see Section 7.2):

- A decrease in platelets to low levels resulting in bleeding has been observed with other ASOs. Subjects must have normal platelet levels upon entry into the trial, and will be monitored throughout the trial (see also Sections 4.1 and 7.11). In addition to central laboratory testing, platelet counts will be performed locally before investigational medicinal product (IMP) administration at the time points specified in the [TRIAL SCHEDULES](#) and before performing a muscle biopsy.
- ASOs are generally directed to the liver, and transient elevation of liver enzymes may be observed as a result. Subjects will be excluded from this trial if they have clinically significant evidence of liver disease. In case any liver abnormalities are observed at baseline, there should be a medically plausible reason for these abnormalities, and a discussion with the medical monitor should occur in this situation before the subject may be dosed for the trial). Liver enzymes will be closely monitored throughout the trial (see also Sections 4.2 and 7.11).
- ASOs are metabolized by cellular endonucleases and the metabolites are then excreted by the kidneys. Estimated glomerular filtration rate (eGFR) must be within normal range upon inclusion into the trial and will be monitored throughout the trial (see also Sections 4.1 and 7.11). Any abnormal results of these tests should have a medically plausible reason and should be discussed with the medical monitor before the subject may be screened and/or dosed for the trial.

Infusion reactions after ASO administration have been known to occur, and are possibly related to complement activation, resulting in local inflammation at the injection site. The DYN101 infusion will be given at a slow rate over 1 hour to minimize the potential of an infusion reaction. Additionally, complement factors will be assessed after each SAD infusion and repetitively during the MAD and extension phase (refer to [TRIAL SCHEDULES](#)).

Should there be significant infusion reaction symptoms, the infusion should be paused for 30 minutes and then restarted at half the rate. If this is still followed by symptoms, the subject should be treated per local standard practice (e.g. a steroid bolus), or the infusion should be stopped altogether.

In addition, several safety measures have been proposed to minimize risk to subjects, including:

- Utilization of selection criteria which exclude subjects who may potentially be at higher risk of an AE (refer to Section 4).
- Utilization of withdrawal criteria (refer to Section 4.5). Subjects withdrawn from IMP or from the trial (except when due to withdrawal of consent), will be encouraged to complete the assessments of the early discontinuation visit (refer to Section 6.1.5).
- AEs assessed as “related” to IMP and all serious adverse events (SAEs) and AEs of special interest (regardless of their relationship to IMP) still ongoing after end of trial participation should be followed on a regular basis according to the investigator’s clinical judgment until the condition is stable (refer to Section 7.10).
- Close monitoring and careful dose escalation as well as the implementation of an IDMC (see Sections 3.1.1 and 9.12).
- The dosing schedule takes into account the possible side effect of C_{max} exposures (t_{max} expected: 2-4 hours) and the observed high plasma exposures (during distribution phase) (see IB, [Dynacure](#)). The distribution phase lasts approximately 24-48 hours. Therefore, the medical monitor will review the 48-hour safety data of the first subject in a cohort before the next subject can be dosed, and there will be an interval of 7 days between dosing of the first and second subject in a cohort (see Section 3.1.1), to see if any delayed toxicities occur. In addition, any SAE data from the first subject received up until the moment of treatment of the second subject will be taken into account.
- Safety evaluations will be done at several time points throughout the trial (refer to the [TRIAL SCHEDULES](#)). Blood samples for biochemistry and hematology (including platelet counts), coagulation tests, complement tests, and urine samples for urinalysis will be collected. Vital signs and triplicate 12-lead electrocardiograms (ECGs) will be recorded, as well as ECG monitoring which will be performed during the single dose infusion (see Section 6.2.2.5). Physical examinations will be performed. In addition, liver ultrasound including hepatic elastography will be performed. IMP can be stopped or interrupted at the investigator’s discretion (refer to Sections 4.5 and 7.11.2).
- For all subjects, there are pre-specified rules that would result in pausing/stopping of IMP administration if predefined conditions occur, preventing exposure of further subjects to IMP until the IDMC has reviewed all safety data (refer to Section 7.11.1).
- The blood sample collection scheme is designed to perform the safety, tolerability and PK (optional for biomarkers and DNA) assessments with a minimum number of blood samples being collected. The total blood volume to be collected is considered to be within the limits of standard blood donation (refer to Section 6.2.86.2.7). Blood samples will be collected by indwelling catheters to minimize discomfort and distress due to repeated venipunctures for blood sampling.
- Pregnancy and breastfeeding are exclusion criteria. In addition, all subjects are required to use contraceptive methods, as detailed in Section 4.3.

More detailed information about the known and expected benefits and risks of DYN101 can be found in the IB for DYN101 ([Dynacure](#)).

